8.5.4 Vital signs

Vital sign parameters to be summarized include systolic blood pressure (SBP), diastolic blood pressure (DBP), body temperature, body weight, respiration rate and pulse rate.

Vital sign parameters collected at each visit/time-point, and its change from baseline to each post-baseline visit (for BNT411 infusion days the value collected pre-infusion will be used for this summary) will be summarized using descriptive summary statistics for each parameter by cohort and visit for each trial part.

Vital sign parameters collected on BNT411 infusion days and its change from baseline (pre-infusion value at that visit) to each post-baseline time-point will be summarized for each time-point using descriptive summary statistics for each parameter by cycle, cohort, and trial part.

Body weight, which is collected at screening and at the beginning of each cycle of treatment, will be summarized using descriptive summary statistics by cycle, cohort, and trial part.

All vital sign data will also be presented in a data listing.

8.5.5 ECG

Triplicate (during trial treatment) or single (at other time points) 12-lead ECG will be collected as shown in CTP Table1-4 and Table 1-5.

The triplicate ECG values will be listed only. For the summary at each time-point, the first assessment will be considered.

ECG variables to be summarized include heart rate, QRS, QTc, QTcF. Absolute values collected at each time-point, and its change from baseline to each post-baseline time-point (for BNT411 infusion days the value collected pre-infusion will be used for this summary) will be summarized using descriptive summary statistics for each parameter by cohort, visit and trial part.

ECG variables collected on BNT411 infusion days and its change from baseline (pre-infusion value at that visit) to each post-baseline time-point will be summarized for each time-point using descriptive summary statistics for each parameter by cycle, cohort, and trial part.

In addition, the number of patients with abnormal QT, and QTcF (number of patients in the following categories ≤ 450 ms, $450\text{-}480$ ms, $480\text{-}500$ ms, >500 ms, and increase ≤ 30 ms, $>30\text{-}60$ ms and >60 ms over baseline) will be summarized by cohort and visit for each trial part.

Additionally, the results of ECG interpretation (normal, abnormal not clinically significant or abnormal clinically significant) will be summarized with number and percentage of patients by cohort and visit. For the triplicate assessments, only the first assessment will be considered for the summary.

A listing of ECG data will also be provided.

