Day	≤21 days prior to Visit C1D 1	D1	D2 b	D3	D8	D1 5	D1	D2 b	D3 b	D1 c, e	-	30 days after last dose	60 days after last dose	-
Before BNT411 infusion (on infusion days) or on day of visit	E1	X, E3,U a	X, E3,U a	X, U a	X, E3	X	X, E3,U a	X, (E3),U	X	X, E3	X, E1	X, E1	X, E1	X, E1,U
Start of infusion		Ud												
End of infusion (+5 min)		X, E3			X, E3		X, E3			X,E3				
Start of infusion + 1 hour (±5 min)		X					(X)							
Start of infusion + 2.5 hours (±10 min)		X			X		X			X				
Start of infusion + 4 hours (±15 min)		X			X		X			X				
Start of infusion + 6 hours (±15 min)		X, E3 a,			X		X, E3ª			(X)				
Start of infusion + 8 hours (±15 min)		X					(X)							

Note: Time points for blood and urine sampling are to be followed as closely as possible but time deviations no longer than 2 hours will not be reported as protocol deviations as long as the exact times of sampling and dose are known.

E1 – Single ECG assessment.

E3 – Triplicate ECG assessments.

X – Blood sampling.

U – Urine sampling.

UNS - Unscheduled visit.

- (X) Blood sampling will only be performed in potential additional patients enrolled to expand the cohorts for RP2D confirmation.
- (E3) Triplicate ECG assessment will only be performed in potential additional patients enrolled to expand the cohorts for RP2D.

<sup>a Sampling time and sample volume have to be documented.

<sup>b Time window for the Day 2 sample in the dose escalation is 24 hours  $\pm$  1 hour and for Day 3 sample is 48 hours  $\pm$  2 hours after the start of infusion on Day 1.

<sup>c PK and ECG must be obtained in Cycle 3, Cycle 5, Cycle 7, and every 4 cycles thereafter (i.e., Cycles 3, 5, 7, 11, 15, etc.). d 6-hour urine collection after start of BNT411 infusion and total volume collected should be documented.

<sup>e After C3D1, PBMCs (for immune phenotyping and TCR profiling) will no longer be collected. Collection of PMBCs at treatment discontinuation and/or unscheduled visits is only required if the patient discontinues trial treatment prior to C3D1.

Table 1-4: PK (blood and urine) sampling and ECG assessment in Part 1B

Treatment Cycle	Screening			Cycle 1				Cycle 2	2	Cycle 3 - N	Treatment Discontinuation	Safety follow-up 1	Safety follow-up 2	UNS

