#### 8.6.3 Electrocardiograms

Triplicate (during trial treatment) or single (at other time points) 12-lead ECG will be obtained as outlined in the SoA (see Section 1.3, Table 1-3 and Table 1-4) using an ECG machine that

automatically calculates the pulse rate and measures PR, QRS, QT, and corrected QT (QTc) intervals. For the assessment the subjects will be in the supine position, lying still and quietly until the assessment has been done.

In general, increases in QT/QTc to >500 ms or of >60 ms over baseline are commonly used as thresholds for potentially discontinuing trial treatment; consultation with a cardiologist should be considered for any such increases to determine whether they are clinically significant.

At each time point at which triplicate ECGs are required, 3 individual ECG tracings should be obtained as closely as possible in succession, but no more than 2 minutes apart. The full set of triplicates should be completed in less than 5 minutes.

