8 STATISTICAL ANALYSES

8.1 General considerations

Unless otherwise specified, the details mentioned are for trial Parts 1A and 1B. The summaries will be presented as cohort and total within trial part (Part 1A and Part 1B). The presentation of data for Part 2 will be included in a SAP amendment.

No formal statistical comparisons between cohorts/trial parts will be performed.

Continuous variables will be summarized by cohort and total (as specified) using the following descriptive statistics: number of patients with non-missing data (n), mean, standard deviation (SD), median, minimum (min) and maximum (max).

Categorical variables will be summarized by cohort and total (as specified) presenting absolute and relative frequencies (n and %) of patients in each category and the number of patients with missing data (missing category will be presented if there is one or more missing value). Percentages will be calculated based on the number of patients with non-missing data (n) in the particular analysis set as the denominator. The text (N=xx) in the tables denotes the number of patients in the analysis set within each cohort. For event-driven occurrence data (e.g., adverse event, concomitant medication, etc.) the percentages will be based on the number of patients in the analysis set (N). For reported visit data (e.g., gender, [Eastern Cooperative Oncology Group] ECOG performance status, etc.) the percentages will be based on the number of patients with non-missing values (n).

All data collected during the trial will be listed, the trial day will be presented as appropriate. The data will be sorted by trial part (Part 1A, Part 1B) cohort, patient number cycle (if applicable) and date of assessment (if applicable).

All analyses will be conducted using SAS® version 9.4 or higher.

Baseline is defined as last available value prior to first dose of any trial treatment (i.e., for Part 1A BNT411 and for Part 1B BNT411 or atezolizumab or carboplatin or etoposide).

Generally, if there are multiple assessments available for a particular day, the assessment that is closest to the day (and time if collected) of the first dose of any trial treatment (i.e., BNT411 or atezolizumab or carboplatin or etoposide) will be used as the baseline value in the summary/analyses.

Multiple values at post-baseline visits: if there are multiple post-baseline assessments available within a visit/day, the earliest value and corresponding date/time will be considered.

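### SAP 8.5.5 counts QT/QTcF categories and ECG interpretation per visit; read with the SAP 8.1 earliest-value default, most end-of-infusion and 6-hour ECGs drop out of those counts

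*SAP*

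**What the plan says.** On infusion days the protocol schedules several ECGs within one visit. Tables 1-3 and 1-4 (Protocol 1.3.1) place triplicates before the infusion, at "End of infusion (+5 min") and, on the first BNT411 day of Cycles 1 and 2, at "Start of infusion + 6 hours (±15 min"). Protocol 8.6.3 says that "increases in QT/QTc to >500 ms or of >60 ms over baseline are commonly used as thresholds for potentially discontinuing trial treatment".

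SAP 8.5.5 plans four kinds of ECG summary:

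- Descriptive statistics by visit, with the pre-infusion value used on infusion days.
- Descriptive statistics for infusion days at each time point, covering the values and their change from that visit's own pre-infusion value.
- Counts of patients in QT/QTcF categories, up to >500 ms for the value "and >60 ms over baseline) will be summarized by cohort and visit for each trial part" for the increase.
- The interpretation (normal, or abnormal with or without clinical significance), "summarized with number and percentage of patients by cohort and visit. For the triplicate assessments, only the first assessment will be considered for the summary".

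The section's own selection rule is "For the summary at each time-point, the first assessment will be considered".

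Two general rules in SAP 8.1 bear on this. One is "Baseline is defined as last available value prior to first dose of any trial treatment". The other is that "if there are multiple post-baseline assessments available within a visit/day, the earliest value and corresponding date/time will be considered".

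**The concern.** The category table is the only planned output that counts patients, by dose level, against the two thresholds named in Protocol 8.6.3. A visit with two or three scheduled ECGs has to be reduced to one category per patient, and SAP 8.5.5 does not say how. The only rule in the SAP that answers the question is the SAP 8.1 default, which picks the earliest value and so, on almost every infusion day, the ECG taken before the drug.

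BNT411 is a 30-minute infusion (Protocol 4.4), and the end-of-infusion ECG is paired with a PK sample, so that ECG should lie closest to peak concentration. As a hypothetical case, a patient at 440 ms before the infusion and 510 ms at its end would be counted for that visit as at or below 450 ms. In a first-in-human trial whose primary objective is safety, a QT effect near peak exposure would be under-counted in the table meant to show it.

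**Working it through.** The plan gives no figure to reproduce. The check is a count of scheduled time points, to which the SAP rules are then applied.

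**Inputs.** Mandatory triplicate ECGs in Protocol Tables 1-3 (Part 1A) and 1-4 (Part 1B). The bracketed entries, which apply only to patients added for RP2D confirmation, are left out.

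**Step 1: time points in Cycles 1 and 2.** Each part has 4 pre-infusion or next-day ECGs, 3 at end of infusion and 2 at 6 hours: 4 + 3 + 2 = 9, spread over 4 visit days.

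**Step 2: baseline.**
- Part 1A: the Cycle 1 Day 1 pre-infusion ECG is the last value before treatment. Post-baseline time points: 9 − 1 = 8.
- Part 1B: treatment starts on Day 1 with the other agents, and no Day 1 ECG is scheduled, so baseline is the screening ECG. Post-baseline time points: 9.

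**Step 3: earliest post-baseline value per visit.**

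| Visit | Kept | Left out |
|---|---|---|
| 1A C1D1 | end of infusion | 6 h |
| 1A C1D2 | 24 h | none |
| 1A C1D8 | pre-infusion | end of infusion |
| 1A C2D1 | pre-infusion | end of infusion, 6 h |
| 1B C1D2 | pre-infusion | end of infusion, 6 h |
| 1B C1D3 | 24 h | none |
| 1B C1D8 | pre-infusion | end of infusion |
| 1B C2D2 | pre-infusion | end of infusion, 6 h |

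Part 1A keeps 4 of 8 and leaves out 4 (50%). Part 1B keeps 4 of 9 and leaves out 5 (56%). In Part 1B the Cycle 1 Day 2 value that enters the table precedes any BNT411.

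**Step 4: end-of-infusion and 6-hour ECGs only.** Through Cycle 2 there are 3 + 2 = 5 per patient. Part 1A keeps 1 of 5 (80% left out); Part 1B keeps 0 of 5 (100% left out).

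**Step 5: later cycles.** ECGs are due in Cycles 3, 5, 7, 11, 15 and so on, before and at the end of the infusion. The pre-infusion ECG is always the earlier, so no end-of-infusion ECG is kept. Through Cycle 7 the total is 5 + 3 = 8: Part 1A keeps 1 of 8, Part 1B 0 of 8.

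**Step 6: what the other outputs recover.** The infusion-day table by time point includes absolute values, and SAP 8.1 makes the maximum a standard statistic, so a value above 500 ms could be seen there. It does not give the number of patients. Its changes are from the same visit's pre-infusion value, which equals trial baseline only on Part 1A Cycle 1 Day 1; elsewhere it cannot show a rise of more than 60 ms over trial baseline.

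**The case against.** The strongest counter-argument is that the SAP never says the category table uses the pre-infusion ECG. SAP 8.5.5 has its own rule, framed per time point. Where it wants pre-infusion values only, it says so in brackets, which would be largely redundant if SAP 8.1 already selected them. Taken literally across scheduled time points, SAP 8.1 would also empty the planned tables by time point, so it may have been meant only for repeats. A count of patients with abnormal QT at a visit could further be read as any qualifying value at that visit.

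Part of this stands. The loss is an inference from two provisions read together. But SAP 8.1 refers to a visit or day, not to repeats, and the first-assessment rule chooses a tracing within a triplicate; it does not bring later time points into a table by visit. Even with SAP 8.1 set aside, the SAP does not say whether first, last or worst value classifies the patient.

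The practical effect is also limited. Escalation cohorts have 1 to 6 DLT-evaluable patients, with backfilling to at most 14. Individual outliers are visible in the listings. ECG findings judged clinically significant are AEs (Protocol 10.3.1). The thresholds in Protocol 8.6.3 apply to individual patients whatever this table shows. Protocol 2.1.4.3 reports hERG activity only at about 200 times the anticipated maximum dose. These points lower the urgency but do not supply the missing rule.

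A reader might also infer that the table mostly shows ECGs taken a week or more after the last infusion. In Cycles 1 and 2 it does not. Of the 4 ECGs kept per part, that describes 2 in Part 1A (C1D8, C2D1) and 1 in Part 1B (C2D2). Each part keeps a 24-hour ECG, and the Part 1B gap from Day 2 to Day 8 is 6 days.

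**Conclusion.** The concern holds as an under-specified table whose only applicable default under-counts QT outliers soon after infusion. Followed as written, the category and interpretation counts omit half of the mandatory post-baseline ECG time points of Cycles 1 and 2 in Part 1A and 5 of 9 in Part 1B, and nearly all end-of-infusion and 6-hour ECGs. The visits are also not on a common footing, since Part 1A Cycle 1 Day 1 contributes a post-infusion value and the other infusion visits a pre-infusion one.

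The result assumes that the SAP 8.1 default governs the category table, that ECGs are taken as scheduled, and that RP2D-only ECGs are excluded.

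It would go too far to conclude that post-infusion ECGs disappear from the report: they are listed and summarized descriptively by time point. What is missing is a count of patients against the thresholds. This should be corrected, but it does not affect the DLT evaluation.

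**What to change.** In SAP 8.5.5, tabulate the QT/QTcF categories and the ECG interpretation by cohort, visit and scheduled time point (pre-infusion, end of infusion, 6 hours), and/or add a count of patients by their worst post-baseline value across all scheduled time points. Either change brings in every scheduled post-infusion ECG: 5 of 5 per patient through Cycle 2 and 8 of 8 through Cycle 7. The worst-value count answers the threshold question most directly; the time-point display shows when the change occurs.

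In SAP 8.1, limit the earliest-value rule to repeat assessments at the same scheduled time point. While editing, correct the cross-reference in SAP 8.5.5: it points to protocol Tables 1-4 and 1-5, but the ECG schedule is in Tables 1-3 and 1-4.

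The cost is SAP wording and some extra table rows. The protocol already schedules these ECGs, so no new data are needed.

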8.5.6 Physical examination

A listing of physical examination findings will also be presented.

8.5.7 ECOG performance status

The frequencies and percentages of patient's ECOG performance status will be provided by cohort and visit for each trial part.

Additionally, a shift table from baseline to each post-baseline visit by cohort will be provided.

A listing of ECOG performance status will also be provided.

8.5.8 Eye examinations

The eye examination data will be summarized for the patients by cohort and visit for each trial part.

- Ophthalmologic entry criteria: Presence/absence for each at baseline

- Slit-lamp examination results will be summarized with frequencies and percentages of patients

A listing of eye examination will also be provided.

8.5.9 ECHO and MUGA

ECHO and MUGA data will be listed only.

8.6 Other analyses

8.6.1 Pharmacokinetics

Plasma and urine samples will be collected for measuring concentrations of BNT411 and its metabolites as per the schedule of timing for collection of samples for PK assessments mentioned in Table 1.3 and Table 1.4 of the CTP. For urine sampling, the exact time of sampling and the volume (mL) excreted over each collection interval must be documented. Full pharmacokinetic profiles will be documented in additional patients enrolled to confirm the RP2D. The actual date and time (24-hour clock time) of each sample will be recorded.

Plasma concentrations of BNT411 and its metabolites (if available) will be listed and summarized by cycle, day, nominal time, and cohort for each part of the trial (Part 1A and Part 1B) using descriptive statistics (n, arithmetic mean, SD, coefficient of variation [CV%], geometric mean, geometric CV%, median, minimum, and maximum) for the Full PK analysis set. The geometric CV% will be calculated as the square root of the exponentiated SD of the natural log-transformed data $\text{SQRT}(\exp(sIn^2)-1)$, where appropriate. Mean and individual plots of plasma concentrations will be presented in both the original and semi-logarithmic scales.

All PK parameters will be summarized by cohort for each part of the trial (Part 1A and Part 1B). For $T_{1/2}$, the following descriptive statistics will be calculated, if possible, n, arithmetic mean, median, CV%, SD, minimum and maximum and, for T_{max} , n, median, minimum and max will be calculated. All other PK parameters will be summarized using n, arithmetic mean, SD, CV%, geometric mean, geometric CV%, median, minimum, and maximum.

The following PK parameters will be determined from plasma concentrations of BNT411 after the first dose on Cycle 1 Day 1 (or Cycle 1 Day 2 for Part B):

- AUC_{0-24} : partial AUC from time 0 to 24 hours calculated using the linear-log trapezoidal method.
- AUC_{0-48} : partial AUC from time 0 to 48 hours calculated using the linear-log trapezoidal method.
- $AUC_{0-\text{last}}$: AUC from time 0 to the last measurable time-point calculated using the linear-log trapezoidal method.
- $AUC_{0-\tau}$: AUC from time 0 to the end of the 168-hour dosing interval (τ) calculated using the linear-log trapezoidal method.

- $AUC_{0-\infty}$: AUC from time 0 extrapolated to infinity, calculated as $AUC_{0-\infty} = AUC_{0-\text{last}} + C_{\text{last}}/\lambda_z$, where C_{last} is the last quantifiable (measurable) concentration.
- C_{max} : Maximum (peak) concentration.
- T_{max} : Time of maximum (peak) concentration.
- λ_z : terminal elimination rate constant.
- $T_{1/2}$: terminal elimination half-life computed as $(\ln 2)/\lambda_z$.
- CL: Clearance, calculated as Dose/ $AUC_{0-\infty}$. Dose will be converted, as necessary, to reflect the amount of anhydrous BNT411 administered (molecular weight 439.5579 g/mole).
- V_D : Volume of distribution, calculated as $[CL/\lambda_z]$.

The following PK parameters will be determined from plasma concentrations of BNT411 after the fourth dose on Cycle 2 Day 1 (or Cycle 2 Day 2 for Part B):

- AUC_{0-24} : partial AUC from time 0 to 24 hours calculated using the linear-log trapezoidal method.
- $AUC_{0-\text{last}}$: AUC from time 0 to the last measurable time-point calculated using the linear-log trapezoidal method.
- $AUC_{0-\tau}$: AUC from time 0 to the end of the 168-hour dosing interval (τ) calculated using the linear-log trapezoidal method.
- C_{max} : Maximum (peak) concentration.
- T_{max} : Time of maximum (peak) concentration.
- λ_z : Terminal elimination rate constant estimated by linear regression of log concentration vs. time; at least three data points are required to compute this parameter.
- $T_{1/2}$: Terminal elimination half-life computed as $(\ln 2)/\lambda_z$.
- CL: Clearance, calculated as Dose/ $AUC_{0-\tau}$. Dose will be converted, as necessary, to reflect the amount of anhydrous BNT411 administered (molecular weight 439.5579 g/mole).
- V_D : Volume of distribution, calculated as $[CL/\lambda_z]$.
- $R_{A,C_{\text{max}}}$: Accumulation ratio for C_{max} computed as C_{max} after Cycle 2 Day 1 (or Cycle 2 Day 2 for Part B) divided by C_{max} after Cycle 1 Day 1 (or Cycle 1 Day 2 for Part B).
- $R_{A,AUC}$: Accumulation ratio for AUC computed as AUC_{τ} after Cycle 2 Day 1 (or Cycle 2 Day 2 for Part B) divided by AUC_{τ} after Cycle 1 Day 1 (or Cycle 1 Day 2 for Part B).
- $T_{1/2,\text{eff}}$: Effective half-life for accumulation computed as $\ln(2)\tau/\ln(R_{A,AUC}/[R_{A,AUC}-1])$.

AUC will be computed using the linear-log trapezoidal rule. When necessary, interpolation or λ_z extrapolation may be used to estimate partial AUCs and $AUC_{0-\tau}$. The value of the extrapolated portion of any AUC ($AUC_{\% \text{extrap}}$) will be less than or equal to 20% for the AUC

to be considered well estimated. If this proportion is > 20%, then the values of AUC will be treated with caution. When AUC is calculated and listed, the AUC%_{extrap} will also be listed. Where AUC%_{extrap} >20%, AUC and all related parameters (i.e., CL, V_D) will be presented but excluded from the calculation of summary statistics. All values excluded from the summaries should be flagged in the individual listings with an explanation for the exclusion.

The λ_z will be estimated by log-linear regression of the concentration-time data associated with this phase. The decision as to which data points describe the terminal phase will be reached by inspecting the semi-logarithmic plot of the data, only considering concentrations at time points beyond T_{max}. A minimum of three data points will be used for the estimation of λ_z preferably covering a time span of at least two half-lives. Ideally, the adjusted r² value of the estimated λ_z will be > 0.80. If λ_z is poorly estimated (i.e., if a time span of at least two half-lives is not used or adjusted r² ≤ 0.80), the corresponding T_{1/2} and other parameters derived using λ_z (i.e., AUC_{0-inf}, CL, and V_D) will be flagged in the report and excluded from summaries for PK parameters dependent on λ_z .

In addition to the two plasma PK profiles collected for doses administered on Cycle 1 Day 1 (or Cycle 1 Day 2 for Part B) and Cycle 2 Day 1 (or Cycle 2 Day 2 for Part B), sparse PK samples will be collected at additional times throughout the trial (see CTP Table 1-3 and Table 1-4). Concentrations of BNT411 in pre-dose samples will be considered C_{trough} values provided they are collected between 156 and 180 hours after the start of the prior dose (i.e., 168 ± 12 hours). Concentrations of BNT411 collected within 5 minutes after the end-of-infusion will be considered end-of-infusion concentrations (C_{eoI}). Values of C_{trough} and C_{eoI} will be summarized longitudinally in tabular and graphical format by nominal elapsed time since the start of first infusion of BNT411.

After a pre-dose void, all urine will be collected over the interval 0 to 6 hours after the start of dosing on Cycle 1 Day 1 in Part 1A and Cycle 1 Day 2 in Part 1B. Actual start and end times and total volumes of urine collections will be recorded.

The following PK parameters will be determined from urine volumes (V_u) and BNT411 concentrations (C_u) on Cycle 1 Day 1 and Cycle 2 Day 1 of Part 1A and Cycle 1 Day 2 and Cycle 2 Day 2 of Part 1B:

- Ae₀₋₆: amount of BNT411 excreted in urine over the collection interval between start and end times calculated as C_u × V_u for the interval.
- fe₀₋₆: fraction of the administered BNT411 dose excreted in urine over the collection interval between 0 and 6 hours calculated as Ae_{t1-t2}/Dose. Dose will be converted, as necessary, to reflect the amount of anhydrous BNT411 administered (molecular weight 439.5579 g/mole).
- CL_{R,0-6}: renal clearance of BNT411 over the collection interval between 0 and 6 hours calculated as Ae₀₋₆/AUC₀₋₆. Partial AUCs will be computed for plasma as described above.

Since BNT411 cannot be present in urine until after dosing, the start of the 0- to 6-hour urine collection interval will be the start of BNT411 infusion at Cycle 1 Day 1 in Part 1A or Cycle 1 Day 2 in Part 1B.

BNT411 dosing and concentration data will be combined with relevant extrinsic and intrinsic covariates and used to develop a population-based pharmacokinetic (PopPK) model suitable for subsequent simulation and exploration of exposure-response trends. The methods to be used in the development of the PopPK model, and its subsequent application, will be described in a separate Modeling and Simulation Analysis Plan (MSAP) and results reported in a separate PopPK report.

Treatment of outliers:

Individual concentration-time points, if considered anomalous, may be excluded from the analysis at the discretion of the pharmacokineticist following a review of the available documentation. Any such exclusion will be discussed with BioNTech and clearly outlined in the trial report.

Entire individual treatment profiles for a patient may be excluded following review of the available documentation and discussion with the sponsor. However, results of analysis with and without the excluded profiles may be presented in the trial report. Any such exclusion will be clearly listed in the trial report along with justification for exclusion.

Non-quantifiable concentrations:

All concentration values reported as no results (not collected or not determined) values will be treated as missing. For the calculation of concentration summaries, all concentrations below the quantifiable limit (BLQ) will be treated as 0. For the purpose of calculating PK parameters and plotting mean and individual concentration-time profiles, BLQ values will be treated as 0 prior to the first measurable concentration. After the first measurable concentration, subsequent BLQ values within the PK profile will be treated as missing. Descriptive statistics at any point will only be calculated if at least 2/3 of the individual data were measured and were quantifiable.

Dose-proportionality analysis:

The dose-proportionality of the PK parameters $AUC_{0-\text{last}}$, $AUC_{0-\text{inf}}$, and C_{\max} for the single-dose PK profile and $AUC_{0-\tau}$ and C_{\max} for the multiple-dose PK profile will be investigated over the administered dose range using the following power model,

$\ln(\text{parameter}) = a + b * \ln(\text{dose})$, where a is the intercept and b is the slope.

Dose proportionality will be assessed for Cycle 1 Day 1 (or Cycle 1 Day 2 for Part B) and Cycle 2 Day 1 (or Cycle 2 Day 2 for Part B) of the trial separately.

Each log-transformed PK parameter will be fit with a power model with a fixed effect term for log-transformed dose. For each PK parameter, the slope and associated 90% CI will be presented. Dose proportionality will be assessed based on whether the 90% CI includes 1.0.

